**Other Secondary Endpoints (Efficacy)**

- Proportion of patients with one point improvement from baseline in clinical status assessment at days 4, 7, 15, 21, 29 using the 7-point ordinal scale
- Mean change in the 7-point ordinal scale from baseline to days 4, 7, 15, 21, 29 (or until discharge)
- Time to resolution of fever defined as body temperature ( $\leq 36.6^{\circ}\text{C}$  [axilla], or  $\leq 37.2^{\circ}\text{C}$  [oral], or  $\leq 37.8^{\circ}\text{C}$  [rectal or tympanic]) for at least 48 hours without antipyretics or until discharge, whichever is sooner
- Time to resolution of fever (as defined above) and improvement in oxygenation (as defined below)
- Days with fever ( $>37.4^{\circ}\text{C}$  [axilla], or  $>38.0^{\circ}\text{C}$  [oral], or  $>38.4^{\circ}\text{C}$  [rectal or tympanic]) based on maximum value observed during a 24-hour period
- Time to change in NEWS2 from baseline
- Time to NEWS2 of  $<2$  and maintained for 24 hours
- Mean change from baseline to days 4, 7, 15, 21, 29 in NEWS2
- Time-to-improvement in oxygenation ( $[\text{SpO}_2]/[\text{FiO}_2]$  of 50 or greater) compared to the nadir for at least 48 hours, or until discharge, whichever is sooner
- Alive off supplemental oxygen at day 29
- Days of hypoxemia ( $\text{SpO}_2 < 93\%$  on room air, or requiring supplemental oxygen, or mechanical ventilatory support)
- Days of supplemental oxygen use
- Days of resting respiratory rate  $>24$  breaths/min (maximum value if recorded at more than once a day)
- Time to oxygen saturation  $\geq 94\%$  on room air
- Ventilator free days in the first 28 days (to day 29)
- Initiation of mechanical ventilation, non-invasive ventilation, or use of high flow nasal cannula (for those not requiring these interventions at baseline)
- Proportion of patients requiring rescue medication during the 28-day period

- ICU status (among those not in an ICU at baseline, record if transferred to the ICU or the need to transfer to the ICU [if the ICU is not available])
- Days of hospitalization among survivors

---

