2.1.3.2 Secondary efficacy endpoint(s)

The key secondary endpoint is the proportion of patients alive at Day 29.

Other secondary endpoints are:

1. Proportion of patients with one-point improvement from baseline in clinical status assessment at days 4, 7, 15, 21, 29 using the 7-point ordinal scale
2. Mean change in 7-point ordinal scale from baseline to days 4, 7, 15, 21, 29 (or until discharge)
3. Time to resolution of fever defined as body temperature ($\leq 36.6^{\circ}\text{C}$ [axilla], or $\leq 37.2^{\circ}\text{C}$ [oral], or $\leq 37.8^{\circ}\text{C}$ [rectal or tympanic]) for at least 48 hours without antipyretics or until discharge, whichever is sooner
4. Time to resolution of fever (as defined above) and improvement in oxygenation (as defined below)
5. Days with fever ($>37.4^{\circ}\text{C}$ [axilla], or $>38.0^{\circ}\text{C}$ [oral], or $>38.4^{\circ}\text{C}$ [rectal or tympanic]) based on maximum value observed during a 24-hour period.
6. Time to change in National Early Warning Score 2 (NEWS2) from baseline
7. Time to NEWS2 of <2 and maintained for 24 hours
8. Mean change from baseline to Day 4, 7, 15, 21, 29 in NEWS2
9. Time to improvement in oxygenation (SpO₂/FiO₂ of 50 or greater) compared to the nadir for at least 48 hours, or until discharge, whichever is sooner
10. Alive off supplemental oxygen at Day 29
11. Days of hypoxemia (SpO₂ $<93\%$ on room air, or requiring supplemental oxygen, or mechanical ventilatory support)
12. Days of supplemental oxygen use
13. Days of resting respiratory rate >24 breaths/min (maximum value if recorded at more than once a day)
14. Time to saturation $\geq 94\%$ on room air
15. Ventilator free days in the first 28 days (to Day 29)
16. Initiation of mechanical ventilation, non-invasive ventilation, or use of high flow nasal cannula (for those not requiring these interventions at baseline)
17. Proportion of patients requiring rescue medications during the 28-day period
18. ICU status (among those not in an ICU at baseline, record if transferred to the ICU or the need to transfer to the ICU [if the ICU is not available])
19. Days of hospitalization among survivors

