2.3.1 Efficacy populations

2.3.1.1 *Intent-to-treat/Modified intent-to-treat population*

The intent-to-treat population (ITT) is the randomized population analyzed according to the treatment group allocated by randomization.

The modified intention-to-treat (mITT) population includes all randomized patients who received at least one dose of the study drug. Analysis of the mITT population will be done according to the initial treatment assigned to the patient (as randomized). The mITT population will be the primary population for analysis of primary and secondary efficacy endpoints, as well as for data including (but not limited to) demographics and baseline characteristics.

2.3.1.2 *Per-protocol population*

The Per Protocol population set (PPS) includes all ITT patients who did not have any relevant major protocol deviations, eg, patients who are randomized and treated, but do not have laboratory-confirmed SARS-CoV-2 infection will be excluded from PPS. The final determination of the exclusion of patients from the PPS will be made prior to the primary database lock. Analysis of the PPS will be done according to the treatment the patient received. The PPS will be used as sensitivity analysis for the primary efficacy endpoint.

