For patients who die, the clinical status recorded on the day of death will be replaced with “1=Death” and this value will be carried forward for all subsequent study days until end of study (Day 60). Death date may be obtained from Adverse Events or Disposition CRFs or phone call at Day 60 (end of study).

For patients who discharge early (other than death), the clinical status recorded on the earliest hospital discharge date will be replaced with 7 (not hospitalized), and this value will be carried forward for all subsequent study days until end of study (Day 60). Hospital discharge information (discharge date and discharge reason) may be obtained from the Discharge Reason eCRF. If there is subsequent hospitalization, the clinical status will not be replaced by 7 after the second hospitalization.

Handling of missing data on clinical status assessment (post-baseline)

For patients who are alive and not discharged (ie, still hospitalized), missing clinical status value (ordinal scale) on a given study day will be imputed using data on the type of oxygen delivery device used by the patient on that day (last type of device used if multiple types were used in a day).

Clinical status = 2 (if using invasive mechanical ventilation or ECMO), or
= 3 (if using non-invasive mechanical ventilation or high-flow nasal cannula), or
= 4 (if using nasal cannula, simple face mask, or non-rebreather face mask) or
= 5 (if not using supplemental oxygen)

Sensitivity analysis

The PPS and ITT will be used for sensitivity analysis of the primary efficacy endpoint, as described above.

Subgroup analyses

Descriptive analyses will be performed on the primary endpoint to summarize the treatment effect of each sarilumab dose versus placebo by the following variables:

- Age (<median, >=median)
- Age group (≥ 18 and < 64 , ≥ 65 and < 84 , ≥ 85 years)
- Sex (Male, Female)
- Race (White, Black or African American, Asian, Other). Note: Japanese will be grouped with Asian, a group with less than 5 patients in any treatment may be grouped with 'Other'
- Ethnicity (Hispanic or Latino, Not Hispanic or Latino)
- Severity of illness (per IRT) (Severe, Critical)
- Severity of illness (as recorded on CRFs) (Severe, Critical)
- Systemic corticosteroids use (per IRT) (Yes, No)
- Systemic corticosteroids use (as recorded on CRFs) (Yes, No)
- Fever status at baseline (Yes, No)
- Pneumonia present based on historical chest X-Ray, CT scan or MRI or lung auscultation (Yes, No)

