Patients who achieved resolution of fever or discharge (other than death) will be considered as events, while patients who do not experience resolution of fever will be censored at the end of study. Patients who started rescue therapy or died in the study will not be considered as having an endpoint event and will be censored at the earlier date of death or rescue therapy start date. Patients who do not have fever at baseline will be censored at the first dose date.

Analysis of endpoint #5: the number of days with fever

Fever is defined as body temperature $>37.4^{\circ}\text{C}$ (axillary), or $>38^{\circ}\text{C}$ (oral), or $>38.4^{\circ}\text{C}$ (rectal or auricular).

The number of days with fever will be analyzed using the ANCOVA model with treatment group and randomization strata as fixed effects for patients alive by Day 29. The LS treatment mean difference from placebo with standard error, along with corresponding 95 % confidence interval and p-value will be provided.

Summary statistics with mean, median, standard deviation, minimum and maximum will be provided. Histogram will be provided to illustrate the distribution of days with fever.

In addition, the percent of days with fever ($100 \times$ number of days with fever divided by number of days of follow-up, defined as the earlier date of death or discharge or last visit up to Day 29) for all patients, will be analyzed using the ANCOVA model with treatment group and randomization strata as fixed effects.

Improvement in Oxygenation

Improvement in oxygenation is defined as increasing in SpO₂/FiO₂ of 50 or greater compared to the nadir SpO₂/FiO₂. Nadir SpO₂/FiO₂ is the nadir (lowest value) at any point in the study, and looking forward, an improvement in oxygenation is increase of 50 or greater from nadir value for at least 48 hours. If nadir is observed on 2 or more different days post baseline, the day of the first occurrence of nadir will be used.

Baseline SpO₂/FiO₂ ratio is defined as the last available ratio prior to first dose.

Post-Baseline SpO₂/FiO₂ ratio is defined as the worst (minimum) value in each day.

For derivation of FiO₂, please see conversion table in [Section 2.5.2](#).

***Analyses of endpoint #4: time to resolution of fever and improvement in oxygenation,
#9: time to improvement in oxygenation, and
#14: time to saturation $\geq 94\%$ on room air***

The analysis of these endpoints will be performed similarly to the primary endpoint.

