Patients who do not experience the event under analysis will be censored at the last observation time point. Patients who die or take rescue medication in the study without experiencing the event will be censored at the earlier date of death or rescue medication started.

***Analyses of endpoint #11: days of hypoxemia,
#12: days with supplemental oxygen use,
#13: days of resting respiratory rate >24 breaths/min, and
#15: ventilator free days in the first 28 days***

The analysis of these endpoints will be performed using the ANCOVA model with treatment group and randomization strata as fixed effects for patients alive by Day 29. The LS treatment mean difference from placebo with standard error, along with corresponding 95 % confidence interval and p-value will be provided. Patient discharged early will be considered as ventilator free until the next hospitalization (if applicable).

Summary statistics with mean, median, standard deviation, minimum and maximum will be provided. Histogram will be provided to illustrate the distribution.

In addition, the percent of days with each endpoint ($100 \times$ number of days with the endpoint divided by number of days of follow up, defined as the earlier date of death or discharge or last

visit up to Day 29) for all patients, will be analyzed using the ANCOVA model with treatment group and randomization strata as fixed effects.

Analyses of endpoint #10: % of patients alive off oxygenation at Day 29, and #16: % of patients with initiation of mechanical ventilation, non-invasive ventilation, or use of high flow nasal cannula, and

These endpoints will be analyzed using a Cochran-Mantel-Haenszel (CMH) test stratified by randomization strata. The difference in proportions of patients for each Sarilumab dose compared to placebo (sarilumab - placebo), along with associated 2-sided 95% confidence levels, and p-value will be provided.

Bar plots will also be provided to illustrate the difference among treatments.

NEWS2

Please find NEWS2 score calculation and details in [Section 2.5.2](#).

Analyses of endpoint #6: Time to change in National Early Warning Score 2 (NEWS2) from baseline, and #7: Time to NEWS2 of <2 and maintained for 24 hours

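### Five day-count endpoints are tested only in patients alive by Day 29, and for ventilator-free days (#15) the added all-patient percentage does not repair this

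*SAP*

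**What the plan says.** SAP 2.3.1 sets the population: "The mITT population will be the primary population for analysis of primary and secondary efficacy endpoints". In SAP 2.1.3.2 only endpoint #19 is restricted in its definition: "Days of hospitalization among survivors". Endpoints #5, #11, #12, #13 and #15 carry no such restriction there or in Protocol Section 3, Table 2.

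The restriction enters in the analysis text of SAP 2.4.4.2. For #5, "days with fever will be analyzed using the ANCOVA model with treatment group and randomization strata as fixed effects for patients alive by Day 29". For #11, #12, #13 and #15 the analysis is done "using the ANCOVA model with treatment group and randomization strata as fixed effects for patients alive by Day 29". Both paragraphs promise the LS mean difference from placebo with standard error, 95% confidence interval and p-value.

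The same section adds a second ANCOVA in all patients, on the percent of days with each endpoint. The day count is "divided by number of days of follow up, defined as the earlier date of death or discharge or last" visit, up to Day 29. For #15 there is also a discharge rule: "Patient discharged early will be considered as ventilator free until the next hospitalization (if applicable". Neither analysis assigns a value to death. By contrast, the ordinal scale in SAP 2.4.4.1 does: "For patients who die, the clinical status recorded on the day of death will be replaced with" the death category, carried forward.

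**The concern.** Being alive at Day 29 is known only after randomisation, and it is the trial's own key secondary outcome. If sarilumab changes survival, the survivors in each arm are no longer comparable groups, and a difference in their mean days mixes the effect of treatment with a change in who is counted.

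For #15 the distortion can run the wrong way. Patients kept alive by the drug may be those who spend long on a ventilator. They then enter only the sarilumab mean and lower it. If the drug instead causes deaths among such patients, they leave the sarilumab mean and raise it. For #5 and #11 to #13 the direction depends on whether the additional survivors have more bad days than the rest, which the documents do not say.

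At stake are p-values on five other secondary endpoints, most clearly #15.

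**Working it through.** **No figure to reproduce.** The documents give no expected day counts and no mortality rates for these endpoints, so the size can only be illustrated.

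**Survivor-only difference for #15.** All inputs are assumptions:
- placebo survival to Day 29, p = 0.80 (range 0.70 to 0.90);
- mean of 22 ventilator-free days in placebo survivors;
- s = change in survival on sarilumab: 0, 0.02, 0.05 or 0.08;
- v = ventilator-free days, if alive, in the patients whose survival differs: 0, 5 or 10;
- no treatment effect in patients who would survive on either arm.

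Formulas, sarilumab minus placebo:
- survival gain: (22p + sv)/(p + s) - 22
- survival loss: (22p - sv)/(p - s) - 22
- all patients with death = 0: +sv for a gain, -sv for a loss

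For p = 0.80 and s = 0.05, 22p = 17.6. Gain: 17.6/0.85 - 22 = -1.29 (v = 0) and 18.1/0.85 - 22 = -0.71 (v = 10). Loss: 17.6/0.75 - 22 = +1.47 (v = 0) and 17.1/0.75 - 22 = +0.80 (v = 10).

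| s | Gain, survivors only (v = 0 / 5 / 10) | Loss, survivors only (v = 0 / 5 / 10) | All patients, death = 0 (+ for gain, - for loss) |
|---|---|---|---|
| 0 | 0 | 0 | 0 |
| 0.02 | -0.54 / -0.41 / -0.29 | +0.56 / +0.44 / +0.31 | 0 / 0.10 / 0.20 |
| 0.05 | -1.29 / -1.00 / -0.71 | +1.47 / +1.13 / +0.80 | 0 / 0.25 / 0.50 |
| 0.08 | -2.00 / -1.55 / -1.09 | +2.44 / +1.89 / +1.33 | 0 / 0.40 / 0.80 |

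For s from 0.02 to 0.08, p = 0.70 gives -0.33 to -2.26 (gain) and +0.35 to +2.84 (loss). With p = 0.90 the ranges are -0.26 to -1.80 and +0.27 to +2.15. The survivor-only difference has the opposite sign to the survival effect throughout. With death = 0 the difference has the same sign as the survival effect, or is zero.

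**The all-patient percentage for #15.**
- Never ventilated, dies on Day 4: 4/4 = 100% ventilator-free, if the day of death counts (the SAP does not say). A survivor in hospital throughout and ventilated for 10 of 28 days scores 18/28 = 64%.
- Discharged on Day 8, never ventilated: crediting the days at home, as the discharge rule requires, gives 28/8 = 350%. Not crediting them departs from that rule. Numerator and denominator cannot both stand as written.

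**The percentage for #11 and #12.**
- On oxygen every day until death: 100%, the worst value. Death is therefore not rewarded here.
- Five oxygen days and discharge on Day 6: 5/6 = 83%. Twenty oxygen days and still in hospital on Day 29: 20/29 = 69%. The shorter course scores worse because discharge cuts the denominator. Over a fixed 28 days, with the home days taken as free of oxygen, the order reverses: 5/28 = 18% and 20/28 = 71%.

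**The case against.** The strongest reply is that the SAP already has an all-patient analysis. It removes the exclusion of deaths, and a reader might infer that it fails equally for all five endpoints. The documents do not support that reading. Entry requires oxygen, ventilatory support or need for intensive care (Protocol 5.1), so many patients who die will have been on oxygen to the end, and for #11 and #12 they score the worst percentage. The remaining fault there is mainly the treatment of early discharge.

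The percentage also limits false conclusions on #15. In a simulation on assumed inputs (160 versus 80 patients, mortality 8% on sarilumab versus 15% on placebo, saved patients ventilated 15 to 28 days, a t-test in place of ANCOVA), the survivor-only difference averaged -1.39 days and was significant against the drug in 24% of runs. The percentage averaged -1.69 points and was significant against the drug in 5%. Death = 0 gave +0.41 days. So the percentage cuts false significance sharply, yet its estimate still has the wrong sign.

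Other points stand. These endpoints lie outside the testing hierarchy (SAP 2.4.4.3), and Protocol 9.4.3.1 plans only median days with quartiles for durations. Death is counted in the ordinal scale, in Day 29 survival with its Kaplan-Meier and Cox analyses, in #10 (alive off oxygen) and in the summary of patients who died or were on a ventilator. Endpoint #16, initiation of ventilation or high-flow oxygen, has no survivor restriction. A survivor-only summary is also legitimate as description; the objection is to attaching a treatment-effect p-value to it.

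**Conclusion.** The concern holds, most clearly for #15. There the main analysis conditions on an outcome that treatment may change, and the supporting percentage neither gives death an unfavourable value nor agrees with the SAP's own discharge rule. Under the stated assumptions a 5-point survival gain moves the survivor-only difference by -0.7 to -1.3 days and a 5-point loss by +0.8 to +1.5. With equal survival the shift is 0. The true size is unknown, and none is claimed for #5, #11, #12 or #13.

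A reader might go further and infer that the trial's main conclusions are at risk, or that all five p-values are known to be wrong. Neither follows. The primary and key secondary analyses do not use this subset, and any bias depends on a survival difference that the documents do not quantify. Nor do the documents show that rank tests, or composites ranking death worst, are required for every endpoint. Those are choices among acceptable methods. The change should be made, but it concerns secondary results.

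**What to change.** **#15.** Make the main analysis all mITT patients over a fixed 28-day window. Score death by Day 29 as 0 ventilator-free days, keep the existing post-discharge rule, and stratify as planned. A rank test is optional.

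**#5 and #11 to #13.** Label the survivor-only results as conditional on survival and descriptive, drop the treatment-effect p-values, and present them beside Day 29 survival. If the all-patient percentage is kept, use a fixed 28-day denominator for patients discharged alive and state the assumption that days after discharge are event-free until readmission. For #5 and #13 an early death without fever or rapid breathing would still score low, which is a further reason to read these results beside survival.

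**Cost.** SAP wording and programming, with no new data. Endpoint #15 will then combine survival and duration. It cannot separate a death from a survivor ventilated for all 28 days, so a survival gain made up only of such patients shows as 0. Readmission is recorded at the Day 29 call (Protocol 1.3, footnote 4, and 4.1), but the plan does not provide for daily observation of oxygen use or fever at home. Because an unblinded interim report has been reviewed (Protocol 4.3), staff blinded to it should make and document the change.

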1 OVERVIEW AND INVESTIGATIONAL PLAN

1.1 STUDY DESIGN AND RANDOMIZATION

This study is a randomized, double-blind, placebo-controlled, phase 3 trial to evaluate the efficacy and safety of sarilumab in hospitalized adults with severe or critical COVID-19. The study will be conducted in Europe and other countries except in the United States (US) in up to 100 sites.

Approximately 400 patients will be randomized via interactive response technology (IRT) in a 2:2:1 allocation ratio to sarilumab 400 mg IV, sarilumab 200 mg IV, or placebo. Randomization will be stratified by severity of illness (severe, critical) and use of systemic corticosteroids (yes, no), and balanced by region. All patients will receive a single dose of study drug on Day 1. Patients may receive a second dose with study drug (based on the original treatment group assigned) 24 to 48 hours after the first dose, if they meet prespecified criteria in protocol.

Severity of illness categories:

- Severe disease:
 - Requires supplemental oxygen administration by nasal cannula, simple face mask, or other similar oxygen delivery device
- Critical disease:
 - Requires supplemental oxygen requiring delivered by non-rebreather mask or high flow nasal cannula, or
 - Use of invasive or non-invasive ventilation, or
 - Requiring treatment in an intensive care unit.

Patients will be assessed daily while hospitalized. Patients discharged from the hospital prior to Day 29 will be contacted with a follow-up phone call on Day 29 to assess status and occurrence of re-admission to a hospital. Patients will undergo a series of efficacy, safety and laboratory assessments while in the hospital. Serum IL-6 and other markers will be collected and analyzed in a central laboratory. Nasopharyngeal (NP) samples to monitor viral infection and blood samples may be obtained on Day 1 (pre-dose), 4, 7, 15, 29 (or up until the day of discharge if the patient is discharged from the hospital before Day 29). An individual patient will complete the study approximately 60 days from screening to follow-up on day 60 ± 7 days. Patients will not be required to return to the hospital once discharged.

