1.3 DETERMINATION OF SAMPLE SIZE

[figure not shown]
The sample size calculations are performed based on the primary endpoint, the time to improvement of 2 points in clinical status assessment from baseline using the 7-point ordinal scale.

Assuming that accrual duration is 3 months (~90 days) with each patient followed for a period of at least 29 days, the proportions of patients with two points improvement from baseline in clinical status assessment at Day 15 are 45% and 70% for placebo and sarilumab, respectively, a total sample size of approximately 400 patients with a 2:2:1 randomization ratio provides at least 90% power for pairwise comparisons between each sarilumab dose (400 mg IV or 200 mg IV; n~160 each) and placebo (n~80), using a log-rank test of superiority at a two-sided significance level of 0.05. Sample size calculation was performed using PASS 14.

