2.4.4.3 Multiplicity issues

Multiplicity will be controlled for the primary analysis (ie, Day 29). Final analysis (ie, Day 60) will be supportive.

For the primary and key secondary endpoints, multiplicity will be controlled via a hierarchical testing procedure in the following order:

1. Primary endpoint sarilumab 400 mg versus placebo
2. Key secondary endpoint sarilumab 400 mg versus placebo
3. Primary endpoint sarilumab 200 mg versus placebo
4. Key secondary endpoint sarilumab 200 mg versus placebo

If one sarilumab dose is discontinued for safety reasons, then all comparisons versus placebo for that dose will be removed and the remaining comparisons will be tested in the order specified above.

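### As written, the all-patient percentage for ventilator-free days (#15) credits days after discharge but stops its denominator at discharge, so values can exceed 100% and discharge timing dominates

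*SAP*

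**What the plan says.** SAP 2.1.3.2 defines endpoint #15 as "Ventilator free days in the first 28 days (to Day 29"). SAP 2.4.4.2 handles it together with #11, #12 and #13, in three steps.

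- The main analysis is an ANCOVA of the day count, "using the ANCOVA model with treatment group and randomization strata as fixed effects for patients alive by Day 29". The paragraph that sets this out ends with a rule that only #15 needs: "Patient discharged early will be considered as ventilator free until the next hospitalization (if applicable").
- A short paragraph on summary statistics and histograms follows.
- A further paragraph then adds a percentage of days for each of these endpoints. It is calculated in all patients as "number of days with the endpoint divided by number of days of follow up, defined as the earlier date of death or discharge"; the final visit also ends follow-up, with Day 29 the limit. It is analyzed with the same ANCOVA terms.

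The SAP gives no separate numerator for the #15 percentage, no truncation at discharge and no cap. The protocol does not define this percentage; its section 9.4.3.1 says only that durations will be summarized by medians and quartiles.

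**The concern.** The credit rule extends the count of ventilator-free days past discharge. The denominator stops at discharge. If the count from the first rule goes into the percentage unchanged, the two parts of the ratio cover different periods and the result is not a percentage of anything.

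At stake is the only modelled analysis of #15 that includes patients who died, since the day-count ANCOVA is restricted to survivors to Day 29. If one arm discharges patients sooner, its mean percentage rises even when ventilator use is identical, and the output would carry a ventilation label. Time to discharge is already summarized separately at the end of SAP 2.4.4.2, so a second measure of discharge speed adds nothing.

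**Working it through.** **The plan's own figures.** No value is stated for this percentage, so there is nothing to reproduce directly. The plan's one computed figure is the power of at least 90% in SAP 1.3. It reproduces: 80 × 0.45 + 160 × 0.70 = 148 events by Day 15 and an event-rate ratio of 2.01 give 98.0% power by the Schoenfeld formula and 93.4% by Freedman's. The present point does not depend on it.

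**Inputs.** The window is 28 days (SAP 2.1.3.2). The credit after discharge and the denominator are from SAP 2.4.4.2. The Day 29 contact in SAP 1.1, "Patients discharged from the hospital prior to Day 29 will be contacted with a follow-up phone call on Day 29", does not lengthen the denominator, because discharge is the earlier date. I count follow-up to discharge on day D as D days, in line with the SAP 2.4.4 convention for durations (event date minus first-dose date plus one).

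**Formulas**, for a patient discharged alive on day D < 28 with V ventilated days and no readmission:

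- As written: 100 × (28 − V)/D
- Numerator cut at discharge: 100 × (D − V)/D
- Fixed 28-day window: 100 × (28 − V)/28

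| D | V | As written | Numerator cut | Fixed 28 days |
|---|---|---|---|---|
| 5 | 0 | 560% | 100% | 100% |
| 8 | 0 | 350% | 100% | 100% |
| 15 | 0 | 186.7% | 100% | 100% |
| 27 | 0 | 103.7% | 100% | 100% |
| 15 | 10 | 120% | 33.3% | 64.3% |
| 15 | 13 | 100% | 13.3% | 53.6% |
| 20 | 15 | 65% | 25% | 46.4% |

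The first form exceeds 100% when 28 − V > D, that is, when V < 28 − D. For discharge on Day 15 that means up to 12 ventilated days. For never-ventilated patients the value is 2800/D, a function of discharge day alone. If follow-up were counted as D − 1 days, the excess would be larger (Day 8: 2800/7 = 400%).

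**Deaths.** Take an unventilated patient who dies on Day 3, with days after death not credited. The ratio to death is 3/3 = 100%, the best possible score once the numerator is cut at discharge. Over a fixed 28 days it is 3/28 = 10.7%.

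**Effect on arm means (illustration only).** The documents give no discharge distribution. I assumed exponential times to discharge, reaching 45% of patients by Day 15 in one arm and 70% in the other. These are the SAP 1.3 improvement assumptions, borrowed as discharge speeds. I assumed no deaths or readmissions, and the same share of patients ventilated in both arms, for a uniform part of their stay. Each arm had 400,000 simulated patients.

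| Share ventilated | Mean as written, slower / faster arm | Difference as written | Numerator cut | Fixed 28 days |
|---|---|---|---|---|
| 0% | 382.9% / 603.8% | 220.8 points | 0 | 0 |
| 10% | 376.9% / 599.4% | 222.5 | 0.4 | 1.0 |
| 20% | 372.8% / 594.8% | 222.1 | 0.7 | 2.0 |
| 40% | 364.3% / 589.0% | 224.8 | 1.5 | 4.0 |

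The small differences in the last two columns arise because the assumption ties ventilated days to length of stay. Across these settings, 92% to 100% of patients discharged before Day 28 exceed 100%. The rank correlation of the percentage as written with discharge day is −0.94 to −1.00. With ventilated days, where any patient is ventilated, it is −0.16 to −0.47.

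**The case against.** The best defence is that the mismatch depends on how the text is read. The credit rule sits in the paragraph on the survivors' day count. The percentage comes two paragraphs later with its own window, and a percentage of follow-up days is naturally taken to count days inside follow-up. The fever-days percentage (#5) uses the same template and has no such problem. A programmer who cuts the numerator at discharge never sees a value above 100%, and values of several hundred percent would probably be noticed in the first output.

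That reading is possible, but the SAP does not state it. The percentage reuses the number of days with the endpoint without redefining it, and for #15 the only rule for days after discharge is the credit. One patient (10 ventilated days, discharged on Day 15) can score 120%, 33.3% or 64.3% depending on the choice, and a prespecified analysis should not leave that open. The restrictive reading also keeps the 100% score for an unventilated early death.

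Some stronger inferences are not supported:

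- A reader might infer that every early discharge exceeds 100%. The last row of the first table shows otherwise.
- A reader might infer that the measure carries no information on ventilation. That is exact only for never-ventilated patients; otherwise discharge timing dominates without wholly replacing it.
- A reader might infer that #11, #12 and #13 share the fault. They have no credit rule for days after discharge.
- A reader might infer that a formal claim is at risk. It is not: "For the primary and key secondary endpoints, multiplicity will be controlled via a hierarchical testing procedure in the following order", and #15 is not in that order. For the percentage the SAP promises an ANCOVA, but does not repeat the explicit promise of an interval and p-value that it makes for the day count.

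**Conclusion.** The point holds for the SAP as written. For #15 the numerator and denominator of the all-patient percentage cover different windows, and most patients discharged early with little or no ventilation would score above 100%. The single-patient values follow from the SAP's rules and the day-count convention stated above. The arm means rest on assumed discharge and ventilation patterns and show only direction and rough scale.

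The consequence is modest. This is an additional analysis of one of 19 other secondary endpoints. The survivors' day count is unaffected, and new ventilation is also analyzed under #16. It should be corrected because the analysis cannot be interpreted as specified and the correction is cheap; it does not threaten the trial's main conclusions.

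**What to change.** Give the #15 percentage one window for both parts. Preferably, use 28 days for every patient, with:

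- days after death counted as not ventilator free;
- days after discharge counted as ventilator free until any readmission, as now;
- days after readmission counted by recorded ventilator status, with a rule for days with no record, since the protocol's Day 29 call is described as collecting adverse events and readmission history;
- a stated rule for withdrawal before Day 29.

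At minimum, say that the numerator also ends at discharge. That keeps the stated denominator and removes values above 100%, but leaves early unventilated deaths at 100%.

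The cost is a few SAP sentences and a small programming change before the primary database lock. No new data collection is needed.
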